4.3.2 Visit 2 [Day 4 (-1 through +2)] – Call/email

- Memory aid review for solicited symptoms

- Unsolicited symptoms review
- Concomitant medications review
- Post-vaccination asthma clinical symptoms review and symptom scores
 - Asthma control assessment (cACT)
 - PROSE
- Medical services utilization review
- Peak flow measurements
- Parent will be instructed to contact the study staff if the child utilizes medical services, has a new asthma medication prescribed, or experiences a serious adverse event

4.3.3 Visit 3 (Day 8 ± 2) – Call/email

- Memory aid review for solicited symptoms
- Unsolicited symptoms review
- Concomitant medications review
- Post-vaccination asthma clinical symptoms review and symptom scores
 - Asthma control assessment (cACT)
 - PROSE
- Medical services utilization review
- Peak flow measurements
- Parent will be instructed to contact the study staff if the child utilizes medical services, has a new asthma medication prescribed, or experiences a serious adverse event

4.3.4 Visit 4 [Day 15 (- 1 through +2)] – Call/email

- Memory aid review for solicited symptoms
- Unsolicited symptoms review
- Concomitant medications review
- Post-vaccination asthma clinical symptoms review and symptom scores
 - Asthma control assessment (cACT)
 - PROSE
- Medical services utilization review
- Peak flow measurements
- Parent will be instructed to contact the study staff if the child utilizes medical services, has a new asthma medication prescribed, or experiences a serious adverse event

4.3.5 Visit 5 (Day 29 ± 2) – Call/email

- Concomitant medications review
- Medical services utilization review

4.3.6 Visit 6 (Day 44 + 3) – Call/email

- Concomitant medications review

- Medical services utilization review
- Post-vaccination asthma clinical symptoms review and symptom scores
 - Asthma control assessment (cACT)
 - PROSE
- Peak flow measurement
- Administer parent/guardian satisfaction survey

4.4 Assignment of Severity

After informed consent, asthma severity will be classified as previously described. Using the Severity and Control tables shown in the Appendix, subjects will be assessed for severity, and these assessments will be recorded on the Case Report Form.

4.5 Baseline demographic data

All patients enrolled in the study will have baseline demographic and clinical data available from their medical records or they will be obtained at the time of enrollment. These data will include age, gender, height and weight to determine the BMI; history of known asthma triggers, including exercise (i.e., exercise-induced bronchospasm), indoor/outdoor climate (e.g., cold, dry air; thunderstorms), allergies (environmental, food, medication, or other documented allergies); allergy testing results; other pertinent physician-diagnosed health conditions (e.g. gastroesophageal reflux disease); presence of household pets; daycare or school attendance; number of siblings/ persons in the household; and exposure to secondhand smoke in the home or other settings where the subject spends considerable time during the day. These details will be recorded in the Case Report Form for Visit 1. If these data are not available from the clinic record they will be obtained from the parents and entered into the REDCap case report form at the time of enrollment.

4.6 Spirometry

Spirometry will not be performed as a study procedure. All enrolled patients who have routine spirometry performed at baseline, as part of their clinical care, with a commercial spirometer will have that data recorded on the case report form. Recent joint statements issued by the American Thoracic Society (ATS) and the European Respiratory Society (ERS) to standardize endpoints for clinical trials suggested that the measurement of Forced Expiratory Volume in 1 second (FEV₁) in an ambulatory clinic setting provides the best objective measure of airway obstruction, which is the hallmark of asthma exacerbation. The statement also cautioned that the safety of this testing has been widely established and that reproducibility is high. Additional information regarding pulmonary health can also be obtained from the Forced Vital Capacity (FVC) and the ratio of FEV₁/FVC from the spirometry data obtained in the clinic in the patients with asthma. For this study, spirometry data will be collected on all patients who have spirometry performed as standard of care (at any site) at enrollment and during any visit prompted by alterations in PEFr or home questionnaires to verify exacerbation.

4.7 Individual Peak Expiratory Flow Rate (PEFR) Evaluations

Subjects will be trained on the “at home” performance of PEFr using a hand held device purchased by study funds and that subjects will get to keep after completing the study. In addition, for all subjects who have spirometry performed at enrollment, it will be compared to the results obtained by the PEFr studies. Numerous longitudinal asthma studies have utilized the peak flow meter device to monitor control between study visits. The device is inexpensive, its use is easily learned, and it can provide an objective measure of

control of asthma symptoms. While PEFr testing with a peak flow meter is inferior to the determination of FEV1 by spirometry as a measure of airway obstruction, it can be very helpful and additive to home questionnaires in monitoring control. Typically, a subject's PEFr is measured while standing by the highest of 3 efforts. These measurements should be completed in the evening, before taking daily controller medication, to minimize variations that may be influenced by diurnal changes. Additionally, the PEFr maneuver should be attempted after completion of the two asthma surveys to avoid bias in the recording of daily symptoms. All efforts will be made to minimize variation in technique; training in proper peak flow meter use will be accomplished at study enrollment and reviewed/reinforced at each study visit.

For this study, all sites will provide participants with the same model of a digital peak flow meter. This device has an automatic memory of 240 data entries with a time stamp; thus, participants will be instructed to record their daily PEFr data measurements on their memory aid/REDCap until day 15 and again at day 43. The device can also be connected to a computer, and the values can be analyzed by using the Microlife Asthma analyzer software program.^{18,19}

4.8 Vaccine Delivery

Only US-licensed vaccines will be used in this study. The vaccines will be purchased from the study site pharmacies and will be administered by a vaccinator. Because cclIV4 is quadrivalent, using quadrivalent IIV (IIV4) in the comparison group will be used. Preferably, all three sites will use the same vaccines, although if this is not possible, similar products will be chosen. The details from the package inserts of the two proposed vaccines are shown below.

Flucelvax® Quadrivalent

Flucelvax® Quadrivalent is a vaccine indicated for active immunization for the prevention of influenza disease caused by influenza A subtype viruses and type B viruses contained in the vaccine. In the United States, Flucelvax® Quadrivalent is antibiotic-, preservative-, and latex-free. Flucelvax® is the only FDA-licensed formulation of non-egg, cell culture-based inactivated influenza vaccine (ccIIV) [approved for use in children and adolescents](#). The quadrivalent formulation of Flucelvax® (ccIIV4) was approved for use in persons 4 years of age and older on May 23, 2016. Studies in children 4-17 years demonstrated non-inferior immunogenicity and comparable safety when compared to the Flucelvax® (trivalent) vaccine preparation. Data demonstrating a decrease in influenza disease after vaccination of this age group with Flucelvax® Quadrivalent are not available. Clinical benefit of Flucelvax® Quadrivalent for individuals 4 to <18 years of age is inferred from immunogenicity as a surrogate. It is our intention that half of the feasibility study subjects at the three CISA-contracted study sites will be randomized to receive Flucelvax® Quadrivalent vaccine.

FLUARIX® Quadrivalent (Influenza Vaccine) Suspension for Intramuscular Injection

FLUARIX® Quadrivalent is a vaccine indicated for active immunization for the prevention of disease caused by influenza A subtype viruses and type B viruses contained in the vaccine. FLUARIX® Quadrivalent is approved for use in persons 3 years of age and older for intramuscular injection only.

There are multiple brands of inactivated influenza vaccine licensed and recommended for use in children aged 5-11 years, and ACIP does not state a preference. For consistency, Fluarix® Quadrivalent inactivated

[figure not shown]
influenza vaccine (IIV4) will be the preferred brand and formulation of seasonal inactivated influenza vaccine administered to enrolled subjects at all three study centers. However, if for some unforeseen reason Fluarix® Quadrivalent is not available at all study sites, the study site may use any formulation of IIV4 that is indicated for use in the study age-group. If a site needs to use an alternative IIV formulation then that site shall use the same formulation until Fluarix® Quadrivalent vaccine becomes available again, to the extent feasible.

Seasonal Influenza Vaccine Dose 2 considerations for Subjects aged 5-8 years

As stated above, children with persistent asthma aged 5 through 11 years, who have not already received a seasonal influenza vaccine during the 2016-17 influenza season, will be enrolled into this study. The ACIP recommends that children aged 6 months through 8 years receive 2 doses of seasonal influenza vaccine, administered at least 4 weeks apart, if they have not previously received 2 or more total doses of trivalent or quadrivalent influenza vaccine before July 1 of the fall influenza season (For purposes of this study, July 1, 2016 would be used as the cutoff date for the 2016-2017 influenza season). The two doses need not to have been received during the same season or consecutive seasons. See Fig 1, modified from *Prevention and Control of Influenza with Vaccines: Recommendations of the Advisory Committee on Immunization Practices, United States, 2015-2016 Influenza Season*.⁹

Among subjects 5 through 8 years otherwise eligible for enrollment into this study, Vanderbilt, Cincinnati, and Duke will assess during the pre-enrollment process whether one or two doses of seasonal influenza vaccine is recommended for each of these potential study subjects. For the 2016-2017 feasibility, the study sites will enroll children with persistent asthma that have received at least 2 doses of seasonal influenza vaccine during prior influenza season(s), such that only one dose of seasonal influenza vaccine is recommended for

FIGURE 2. Influenza vaccine dosing algorithm for children aged 6 months through 8 years — Advisory Committee on Immunization Practices, United States.

^aThe two doses need not have been received during the same season or consecutive seasons.

^bDoses should be administered ≥4 weeks apart.

the 2016-2017 influenza season. The quadrivalent seasonal inactivated influenza vaccine will be administered at baseline (Day 1 of study) according to the study randomization scheme.

4.9 Monitoring Vaccine Safety in the First 15 Days

On the vaccination day and for the next 14 days post-vaccination, all subjects will be monitored daily by their parents and the information will be recorded using memory aids provided at the enrollment visit. Daily reactogenicity, including measurement of nighttime awakening, and two asthma scoring systems will be completed (cACT score and the PROSE score).

In addition to the two symptom scores above, several predefined events that could occur after vaccine administration will also be recorded for 14 days after vaccination. These will include; fever (oral temperature $\geq 100.4^{\circ}\text{F}$), runny nose/ nasal congestion, sore throat, cough, wheeze, vomiting, change in activity level, appetite change, irritability, abdominal pain/stomachache, headache, chills, and muscle aches. Local reactions after the intramuscular vaccination will also be captured and include: redness, swelling, and/or pain around the injection site. Medication receipt, new prescriptions for asthma medications, and any previously unscheduled healthcare utilization (medical office visits, ED visits, hospitalizations) will also be documented on the reaction form. To ensure compliance with the reaction assessment, parents will be called or emailed through REDCap on Days 4, 8 and 15 by the study staff.

On the day of vaccination and during the first 14 days after vaccination, if the subject reports an increase in their symptoms and an increase in the need for medications for their asthma, the family will be instructed to contact the study staff, so medical records can later be collected, if applicable. If at any point a study participant is experiencing symptoms of any asthma exacerbation, the participant or their parent will be instructed to contact their PCP and inform study staff of this encounter.

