On May 23, 2016, the quadrivalent formulation of Flucelvax[®] Quadrivalent (cclIV4) was approved for use in persons 4 to <18 years of age under the accelerated [approval of biological products regulations](#) (21 CFR 601.40-46). Flucelvax[®] Quadrivalent (cclIV4) is a non-egg, cell culture-based [Madin Darby Canine Kidney cells (MDCK)], non-adjuvanted, inactivated influenza vaccine indicated for active immunization for the prevention of influenza disease caused by influenza A subtype viruses and type B viruses contained in the vaccine. According to the [package insert](#), Flucelvax[®] Quadrivalent is antibiotic-, preservative-, and latex-free. ACIP considers Flucelvax[®] an appropriate option for vaccination in persons aged 4 years and older. Federal funding was provided to develop this non-egg based cell culture technology to allow for rapid scale-up of influenza vaccination production as needed to fulfill the needs during an influenza pandemic. Flucelvax[®] is the only FDA-licensed formulation of a non-egg-based influenza vaccine approved for use in children and adolescents.

The safety of Flucelvax[®] Quadrivalent in children was evaluated in a randomized, double-blind, controlled study conducted in the US. The safety population included a total of 2332 children 4 through 17 years of age; 1161 children 4 through 8 years of age and 1171 children 9 through 17 years of age. In this study, subjects received Flucelvax[®] Quadrivalent or one of the two formulations of Flucelvax[®] (trivalent) influenza vaccine (Flucelvax[®] Quadrivalent n=1159, TIV1c, n=593 or TIV2c n= 580). Children 9 through 17 years of age received a single dose of Flucelvax[®] Quadrivalent or a trivalent Flucelvax[®] formulation. Children 4 through 8 years of age received one or two doses (separated by 4 weeks) of Flucelvax[®] Quadrivalent or a Flucelvax[®] trivalent formulation based on determination of the subject's prior influenza vaccination history. The mean age of subjects who received Flucelvax[®] Quadrivalent was 9.6 years of age. In children ≥ 4 through <18 years of age, for the quadrivalent formulation, the most common injection-site reaction was pain (59%) and tenderness for subjects ≥ 4 to <6 years of age (55%). Most of the solicited local adverse events (AEs) had their onset from 6 hours to 2 days after the vaccination and were mild to moderate in severity. The most common solicited systemic adverse events in children >4 years to < 18 years, that occurred at rates >10%

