were myalgia, headache, fatigue, sleepiness and irritability. Fevers ≥ 38.0 °C occurred in 3% of subjects; one subject who received cclIV4 had a febrile convulsion. In children 4 through 17 years of age, serious adverse events (SAEs) were collected throughout the study duration (until 6 months after last vaccination) and were reported by 0.5%, of the subjects who received Flucelvax[®] Quadrivalent. None of the SAEs were assessed as being related to study vaccine.

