5.2 Inactivated Influenza Vaccine (IIV)

ACIP routinely recommends IIV for children with asthma⁷⁻⁹ and risks after IIV would be no higher than those encountered through usual care. Most people who get a flu shot do not have any problems with it. Minor problems following a flu shot include soreness, redness, or swelling where the shot was given, hoarseness, sore, red or itchy eyes, cough, fever, aches, headache, itching, fatigue. If these problems occur, they usually begin soon after the shot and last 1 or 2 days. More serious problems following a flu shot can include the following: There may be a small increased risk of Guillain-Barré Syndrome (GBS) after inactivated flu vaccine. This risk has been estimated at 1 or 2 additional cases per million people vaccinated, primarily in adults. This is much lower than the risk of severe complications from flu, which can be prevented by flu vaccine. Problems could happen after any injected vaccine: People sometimes faint after a medical procedure, including vaccination. Sitting or lying down for about 15 minutes can help prevent fainting, and injuries caused by a fall. Some people get severe pain in the shoulder and have difficulty moving the arm where a shot was given. This happens very rarely.

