7.2 Termination of Study

This study may be terminated for safety concerns of the PI, CDC, or participating IRBs.

8 Statistical Analytic Plan

This study aims to enroll approximately 50 participants (~20 from Vanderbilt, ~20 from Cincinnati and ~10 from Duke). Since sample-sizes were predetermined and since this is a feasibility study, no power calculations were conducted. All analyses will be performed using R 3.2.3 (r-project.org), SAS version 9.4, or STATA version 14.

Feasibility Analysis

The proportion of children meeting the outlined feasibility benchmarks (Appendix, Table A1) will be determined.

Descriptive Statistics

Descriptive analyses will be summarized for continuous variables with mean, standard deviation, median, and interquartile range. Categorical variables will be summarized with frequencies and percentages. Explanatory figures will be generated to evaluate the data distribution. Comparisons of demographic characteristics between cclIV4 and IIV4 groups will be conducted using Pearson Chi-square and Wilcoxon tests appropriately.

Primary Objective

To assess the feasibility of conducting a randomized prospective safety study of LAIV4 versus IIV4 during the 42 days after vaccination in children aged 5-11 years with persistent asthma of varied severity (cclIV4 will be used as a surrogate for LAIV4)

Primary Outcomes Measures

1. Assess the proportions of those achieving Feasibility Benchmarks (Table A1 Appendix)
2. Qualitatively describe best practices and lessons learned

Secondary Objectives

1. To compare proportions of local and systemic reactogenicity events during the 14 days after cclIV4 versus IIV4 in children with asthma aged 5-11 years.
2. To describe the unsolicited and serious adverse events in children receiving cclIV4 and IIV4 during the 42 days.
3. To compare proportions of asthma exacerbations during the 14 days after cclIV4 versus IIV4 in children with asthma aged 5-11 years.
4. To compare proportions of asthma exacerbations during the 42 days after cclIV4 versus IIV4 in children with asthma aged 5-11 years.
5. To explore differences between the cclIV4 and IIV4 groups regarding clinical asthma symptoms after vaccination and changes in asthma control before and after vaccination in children with asthma of varied levels of severity.

Secondary outcome measures

1. Proportion of subjects with solicited local and systemic reactogenicity events for 14 days after vaccination between recipients of cclIV4 and IIV4.

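### Section 4.9 does not name fatigue or sleepiness among the solicited Day 1-15 events, although the protocol reports both above 10% after the test vaccine

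*Combined protocol and SAP*

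**What the plan says.** The Background summarises the pediatric safety study of the test vaccine. It introduces the main systemic findings with "The most common solicited systemic adverse events in children >4 years to < 18 years, that occurred at rates >10" percent and says that these "were myalgia, headache, fatigue, sleepiness and irritability". These were solicited events in that study.

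Section 5.2, on the risks of inactivated influenza vaccine, gives the minor problems after a flu shot as including "hoarseness, sore, red or itchy eyes, cough, fever, aches, headache, itching, fatigue", as well as local soreness, redness and swelling.

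Section 4.9 says that "several predefined events that could occur after vaccine administration will also be recorded for 14 days after vaccination". The list starts with fever, goes on to "runny nose/ nasal congestion, sore throat, cough, wheeze", and ends with "vomiting, change in activity level, appetite change, irritability, abdominal pain/stomachache, headache, chills, and muscle aches". Local reactions are listed separately. The wording says what the events will include; it does not say that the list is complete.

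Section 8 defines secondary outcome 1 as "Proportion of subjects with solicited local and systemic reactogenicity events for 14 days after vaccination between recipients of cclIV4 and IIV4". Secondary outcome 2 covers unsolicited and serious events, whose nature and frequency are to be described. Sections 4.3.2 to 4.3.4 have staff review unsolicited symptoms at the Day 4, 8 and 15 contacts.

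**The concern.** The plan reports five common systemic reactions to its own test vaccine and then names only three of them in the daily diary list. The other two are subjective, and fatigue is also given as a known reaction in the comparator class.

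The route of collection decides how a reaction is analysed. Solicited events enter a planned comparison of proportions, whereas unsolicited events are only described. A reaction without its own diary item is either folded into a broader item or left for a parent to mention at one of three contacts. In an open-label study, what parents mention unprompted can depend on what they expect of the vaccine. A daily item asked identically in both arms is less exposed to this.

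The Background (section on the feasibility study) gives additional descriptive safety data on this vaccine in children with asthma as one benefit of the study. The natural reference is the pediatric study that the protocol cites. For two of its five commonest systemic reactions, the diary as described would not yield a figure under the same term.

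**Working it through.** **Item-by-item match**

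The left column is from the Background, the right column from section 4.9.

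| Reaction above 10% after ccIIV4 | Solicited item in section 4.9 |
|---|---|
| Myalgia | Muscle aches: named |
| Headache | Headache: named |
| Irritability | Irritability: named |
| Fatigue | Not named; nearest item is change in activity level |
| Sleepiness | Not named; nearest item is change in activity level |

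Section 4.9 has 13 systemic and respiratory items: fever, 4 respiratory and 8 others. Coverage by name is 3 of 5, so 2 of 5 (40%) are not named.

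**Is change in activity level a substitute?** It is solicited daily, and a tired or drowsy child may well score on it. But the plan gives it no definition or direction. The asthma control chart in the Appendix (Figure A1) uses interference with normal activity as a criterion of asthma impairment. In this population a positive answer could therefore mean fatigue, sleepiness, asthma limitation or another illness. The nighttime awakening that section 4.9 also records is a different symptom from daytime sleepiness.

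**Scale**

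The plan states no sample-size, power or alpha figure for this outcome, so there is nothing to reproduce. The figures below are for scale only.

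- Children per arm: about 50 randomized 1:1 (section 4), so 50 / 2 = 25.
- Rate p: the documents say only above 10%, for ages 4 to under 18, and give no rate for each reaction. I assume 10% to 20%.
- Expected affected ccIIV4 children per reaction = 25 × p: 25 × 0.10 = 2.5; 25 × 0.20 = 5.
- Chance of at least one case = 1 − (1 − p)^25: 1 − 0.90^25 = 0.93; 1 − 0.80^25 = 0.996.

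The same count cannot be made for the IIV4 arm. Section 5.2 lists fatigue without a rate and does not mention sleepiness.

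**What a between-arm comparison could show even if both were solicited**

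- Approximate 95% CI half-width with the same rate in both arms = 1.96 × √(2p(1 − p)/25). At p = 0.10: 1.96 × √(0.18/25) = 0.17. At p = 0.20: 1.96 × √(0.32/25) = 0.22.
- Power at an assumed two-sided alpha of 0.05 = Φ[(|p1 − p2| − 1.96√(2p̄(1 − p̄)/25)) / √((p1(1 − p1) + p2(1 − p2))/25)], where p̄ is the mean of p1 and p2. For 10% vs 20%: (0.10 − 1.96 × 0.101)/0.100 = −0.98, so about 16%. For 10% vs 30%, about 42%. For 10% vs 40%, about 70%.

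The gain from naming the items is therefore descriptive: a proportion per arm, under a term that matches the earlier study.

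**The case against.** The strongest case against has five parts.

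1. *The reactions are not lost.* Activity level is solicited every day, and staff review unsolicited symptoms at Days 4, 8 and 15. Section 5.2 says minor problems come early and last a day or two, so the Day 4 contact falls close to them. This stands. A reader might infer that the study misses fatigue and sleepiness altogether, and the documents do not support that. What is lost is the specific term and a systematic daily question.

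2. *The list may not be complete.* Its wording is inclusive, and the memory aid, which is the actual instrument, is not in the documents. This also stands. The supportable claim is that section 4.9 does not name the two reactions, not that parents are never asked about them.

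3. *The item choice fits the purpose.* The study rehearses a later LAIV4 study, and a list weighted to respiratory signs suits that aim and children with asthma. Section 5.2 taken alone would equally call for hoarseness, itchy eyes and itching. This is fair, and it is why the point rests on the Background rather than on section 5.2. The rate above 10% after the vaccine under test sets fatigue and sleepiness apart from the rest of the section 5.2 list.

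4. *The rate is borrowed.* It is for ccIIV4 at ages 4 to under 18, not for ages 5-11, for children with asthma or for IIV4. This stands, and it limits the expected count to one arm and to an assumption.

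5. *The consequence is small.* The list is the same in both arms, so the omission does not by itself bias the comparison of the events that are listed. A comparison on either symptom would be imprecise anyway. Both statements are right, but the descriptive loss does not depend on power.

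**Conclusion.** The mismatch is real. Two of the five systemic reactions that the protocol reports above 10% after its test vaccine are not named among the solicited events. They would not appear as such in secondary outcome 1, and they could not be set beside the earlier pediatric figures. If the pooled rate carries over to this population (assumed 10% to 20%), about 2.5 to 5 of 25 ccIIV4 children would have each reaction. Some would be recorded through the activity item or the unsolicited review.

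Two stronger readings go too far. One is that a similar number would be overlooked in each arm; the documents give no IIV4 rate for either symptom. The other is that the gap hides a between-arm difference the study could otherwise establish; power is about 16% for 10% vs 20%.

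The benchmarks in Table A1, and so the primary outcome, are unaffected. Importance is minor to moderate. The conclusion assumes that the memory aid follows section 4.9 as written.

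**What to change.** Add fatigue/tiredness and sleepiness as separate daily solicited items for Days 1 to 15 in section 4.9, in the memory aid and REDCap diary, and in the events counted under secondary outcome 1 (sections 2.2 and 8). If the memory aid already asks about them, list them in section 4.9 so that the plan and the instrument agree. It would also help to define change in activity level and give its direction. Doing that alone would be weaker, because neither reaction would then have its own figure.

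The list goes from 13 to 15 items, and coverage of the five common reactions from 3 to 5. The cost is two more entries a day for parents, or 2 × 15 = 30 per child over the diary period. That is a small addition to a diary whose completion is itself a feasibility benchmark. Sample size and visits do not change. The change has to be made before data collection, because daily parent-recorded symptoms cannot be recovered reliably afterwards.
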